4.5.1 Dosing

4.5.1.1 Nivolumab plus Ipilimumab (Arm A)

Participants randomized to Arm A will receive treatment with nivolumab 3 mg/kg every 2 weeks as a 30-minute infusion and ipilimumab 1 mg/kg every 6 weeks as a 30-minute infusion, starting on Day 1, until progression, unacceptable toxicity, withdrawal of consent, the study ends, or a maximum of 24 months from the first study treatment, whichever occurs first.

When nivolumab and ipilimumab are to be administered on the same day, separate infusion bags and filters must be used for each infusion. Nivolumab is to be administered first. The second infusion will always be ipilimumab and will start no sooner than 30 minutes after completion of the nivolumab infusion. Participants who require small volumes may infuse over < 30 minutes but no less than 20 minutes. The second infusion will always be the ipilimumab study treatment and will start after the infusion line has been flushed, filters changed and participant has been observed to ensure no infusion reaction has occurred.

Nivolumab and ipilimumab may be diluted in 0.9% Sodium Chloride Solution or 5% Dextrose solution.

Dosing calculations should be based on the body weight. If the participant's weight on the day of dosing differs by > 10% from the weight used to calculate the prior dose, the dose must be recalculated. All doses should be rounded to the nearest milligram. There will be no dose modifications allowed for both nivolumab and ipilimumab.

Participants may be dosed with nivolumab no less than 12 days from the previous dose. There are no premedications recommended for the first dose of study drug.

Participants should be carefully monitored for infusion reactions during nivolumab administration. If an acute infusion reaction is noted, participants should be managed according to [Section 4.5.8](#)

Doses of nivolumab may be interrupted, delayed, or discontinued depending on how well the participant tolerates the treatment. Dosing visits are not skipped, only delayed.

Nivolumab Injection, 100 mg/10 mL (10 mg/mL) is to be administered as an IV infusion through a 0.2-micron to 1.2-micron pore size, low-protein binding in-line filter at the protocol-specified doses. It is not to be administered as an IV push or bolus injection. When the dose is based on patient weight (ie, mg/kg), nivolumab injection can be infused undiluted (10 mg/mL) or diluted with 0.9% Sodium Chloride Injection, USP or 5% Dextrose Injection, USP to protein concentrations as low as 0.35 mg/mL. When the dose is fixed (eg, 240 mg flat dose), nivolumab injection can be infused undiluted or diluted so as not to exceed a total infusion volume of 120 mL. Nivolumab infusion must be promptly followed by flush of diluent to clear the line. Instructions for dilution and infusion of nivolumab injection may be provided in the clinical protocol, pharmacy binder, or pharmacy reference sheet. Care must be taken to assure sterility of the prepared solution as the product does not contain any antimicrobial preservative or bacteriostatic agent.

Nivolumab infusions are compatible with polyvinyl chloride (PVC) or polyolefin containers and infusion sets, and glass bottles.

Ipilimumab injection can be used for IV administration without dilution after transferring to a PVC, non-PVC/non-DEHP or glass container and is stable for 24 hours at 2-8°C or room temperature/room light (RT/RL). For ipilimumab storage instructions, refer to ipilimumab IB and/or pharmacy reference sheets.

Separate infusion bags and filters should be used when administering nivolumab and ipilimumab on the same day.

Ipilimumab is to be administered as a 30 minute IV infusion and may be infused using a volumetric pump with a 0.2 to 1.2 micron low-protein binding in-line filter at the protocol-specified dose. The drug can be diluted with 0.9% normal saline or 5% Dextrose Injection to concentrations between 1 mg/mL and 4 mg/mL. It is not to be administered as an IV push or bolus injections. Care must be taken to assure sterility of the prepared solutions, since the drug product does not contain any antimicrobial preservatives or bacteriostatic agents. At the end of the infusion, flush the line with a sufficient quantity of diluent.

Doses of nivolumab and/or ipilimumab may be interrupted, delayed, or discontinued depending on how well the participant tolerates the treatment. For more details, see [Section 4.5.2](#) (dose delays), [4.5.4](#) (resuming treatment), and [4.5.5](#) (discontinuation).

4.5.1.2 EXTREME Regimen (Arm B)

Participants randomized to Arm B will receive treatment with an initial dose of cetuximab 400 mg/m² (over 2 hours infusion) then weekly 250 mg/m² (over 1 hour infusion) (or every 2 weeks, per local prescribing information), cisplatin (100 mg/m² IV on Day 1) or carboplatin (AUC 5 IV on Day 1) and 5-FU (1000 mg/m² continuous IV from Day 1 to Day 4) every 3 weeks per cycle for a maximum of 6 cycles.

Cetuximab maintenance begins after 6 cycles of the cetuximab, cisplatin or carboplatin, and 5-FU are complete and is considered cetuximab alone at 250 mg/m² weekly (1 hour infusion). Cetuximab maintenance can continue until progression, unacceptable toxicity, withdrawal of consent, or other reason (see [Section 3.5](#) for complete list of reasons for discontinuing study medication).

The dosing calculations should be based on the body weight. If the participant's weight on the day of dosing differs by > 10% from the weight used to calculate the dose, the dose must be recalculated. Doses can be rounded per institutional standards. Participants may be dosed no less than 7 days between doses.

The dose of Carboplatin during chemotherapy will be calculated using the following formula (Calvert equation):

- Carboplatin total dose in mg = AUC x (glomerular filtration rate [GFR] +25)

NOTE: When calculating carboplatin dose, GFR should not exceed 125 mL/min. Thus, the maximum carboplatin dose for AUC of 5 will be 750 mg.

Calculated creatinine clearance (CrCl) will be used to estimate the GFR. The modified Cockcroft-Gault formula below should be used to calculate the creatinine clearance.

- $140 - \text{age (years)} \times \text{actual weight (kg)} / 72 \times \text{Serum creatinine (mg/dL)}$ (for females, multiply the result by 0.85)

The actual weight will be used for the calculation of Creatinine Clearance.

If one of the study drugs is discontinued, the other study drugs may be continued for the remainder of the cycles.

Premedications

For cetuximab:

The recommended premedication is with an H1 antagonist (eg, 50mg Diphenhydramine) IV 30-60 minutes prior to the first dose; for subsequent doses, premedication should be administered based upon clinical judgement and presence/severity of prior infusion reactions in accordance with local institutional standard practice.

For carboplatin or cisplatin:

The recommended premedication are dexamethasone (dosing according to local standard; an equivalent dose of another corticosteroids may be substituted) and a 5-HT3 receptor antagonist (type per investigator discretion and local standards of care) prior to each dose. Additional use of emetics premedication may be employed at the discretion of the investigator. Refer to the local product label for more detail.

For cisplatin:

Hydration guidelines may be modified at the discretion of the treating physician provided adequate pre- and post-cisplatin hydration is achieved, and renal function remains adequate. One suggested regimen consists of administering cisplatin in 500 cc to 1000 cc of IV fluids following adequate hydration and the establishment of adequate urinary output. It is suggested the pre-cisplatin hydration consist of NS at 500 cc/hr x 1 liter and post-cisplatin hydration consist of 1/2 NS + 10 meq KCl/liter + 1 gram magnesium sulfate/liter + 25 grams mannitol/liter at 500 cc/hr for at least one hour, followed by additional hydration at the discretion of the investigator.

It is suggested that patients receive antiemetic therapy, acute and delayed, including dexamethasone, 5-HT3 serotonin receptor antagonists. However, the specifics of the regimen are at the discretion of the treating physician, provided adequate control is achieved. One potential regimen consists of 20 mg of oral or IV dexamethasone and a high dose of oral or IV 5-HT3 antagonist (such as 2 mg oral or 10 mg/kg IV granisetron, or 32 mg oral or IV ondansetron) on the day of cisplatin administration. Followed by additional anti-emetics consisting of oral dexamethasone and scheduled 5-HT3 serotonin receptor antagonists on days 2-5. For example, 8 mg orally, twice daily for days 2 and 3, and then 4 mg orally, twice daily for days 4 and 5, especially if aprepitant is not given.

All supportive measures consistent with optimal patient care should be used throughout the study. Recombinant erythropoietin or similar compound may be administered for symptomatic and/or progressive > Grade 2 anemia. Agents such as G-CSF may also be used at the investigators' discretion.

The use of cisplatin or carboplatin is at the discretion on the investigator. Switch from cisplatin to carboplatin is allowed. If patients develop specific intolerable cisplatin-associated toxicities (see dose modifications, carboplatin substitution), such as neuropathy, renal impairment, ototoxicity, or nausea/vomiting, carboplatin at an AUC of 5 will be substituted for cisplatin.

Doses of cetuximab, cisplatin or carboplatin and 5-FU (EXTREME regimen) may be interrupted, delayed, reduced or discontinued depending on how well the participant tolerates the treatment. For more details, see Sections 4.5.2 (dose delays), 4.5.3 (dose reductions), 4.5.4 (resuming treatment), and 4.5.5 (discontinuation).

Participants should be carefully monitored for infusion reactions. If an acute infusion reaction is noted, participants should be managed according to [Section 4.5.8](#).

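### The optional cisplatin antiemetic example gives IV granisetron per kilogram at 250 to 500 times the oral alternative (50–100 kg), so a figure or unit is very probably wrong as printed

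*Protocol*

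**What the plan says.** Protocol section 4.5.1.2 (EXTREME Regimen, Arm B) has a Premedications part with separate text for cetuximab, for carboplatin or cisplatin, and for cisplatin alone. The cisplatin text offers an example antiemetic regimen for the day of cisplatin. It begins "One potential regimen consists of 20 mg of oral or IV dexamethasone" and adds "a high dose of oral or IV 5-HT3 antagonist", illustrated by "such as 2 mg oral or 10 mg/kg IV granisetron, or 32 mg oral or IV ondansetron".

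The example is not binding. The sentence before it says that "the specifics of the regimen are at the discretion of the treating physician, provided adequate control is achieved". The preceding paragraph, on carboplatin or cisplatin, closes its premedication advice with "Refer to the local product label for more detail".

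Granisetron is mentioned nowhere else in the protocol or the SAP. It is not one of the six investigational products in section 4.1, and section 4.2 allows supportive medication to be treated as non-investigational.

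**The concern.** The text presents "2 mg oral or 10 mg/kg IV granisetron" as a choice of route for one drug, given once for one purpose. A reader would expect the two to be of similar size. One is a flat amount and the other scales with body weight, and at any adult weight the IV amount is hundreds of times the oral amount.

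The other two drugs in the sentence set the pattern. Dexamethasone is 20 mg by either route, and ondansetron is "32 mg oral or IV ondansetron". Only IV granisetron is per kilogram.

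Two features make the figure easy to read past. The sentence announces a high dose, so a large number may look intended. And mg/kg is a familiar unit in this protocol, because nivolumab and ipilimumab are dosed that way. If a site copied the IV figure without checking a label, a participant would be given several hundred milligrams where the stated oral alternative is 2 mg.

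**Working it through.** **Inputs**

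- Granisetron oral: 2 mg flat (section 4.5.1.2).
- Granisetron IV: 10 mg/kg (same sentence).
- Dexamethasone: 20 mg by either route (same sentence).
- Ondansetron: 32 mg by either route (same sentence).
- Body weight: not given in the documents. Assumed 50–100 kg, with 40–120 kg as a wider check.
- Arm B size: 930 randomized 1:1, so 930 / 2 = 465 (section 3.1).

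**Formulas**

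IV dose (mg) = 10 mg/kg × weight (kg). Ratio = IV dose / 2 mg.

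| Weight (kg) | IV dose as printed (mg) | Ratio to 2 mg oral |
|---|---|---|
| 40 | 400 | 200 |
| 50 | 500 | 250 |
| 70 | 700 | 350 |
| 100 | 1000 | 500 |
| 120 | 1200 | 600 |

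**Weight at which the two agree**

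2 mg / 10 mg/kg = 0.2 kg. No adult weight reconciles them.

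**IV-to-oral ratio within the same sentence**

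- Dexamethasone: 20 / 20 = 1.
- Ondansetron: 32 / 32 = 1.
- Granisetron: 250 to 500 at 50–100 kg.

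**Illustration of one possible slip**

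If the unit were microgram/kg, the IV dose would be 10 × 50 / 1000 = 0.5 mg to 10 × 100 / 1000 = 1.0 mg. That is 0.25 to 0.5 times the oral figure, so the two would be of the same order. This reading is an assumption that the documents do not confirm.

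**Could this be a fault in reading the PDF?**

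A micro sign misread as m would produce exactly this text. Against that, the micro symbol is preserved elsewhere in the protocol: in the haematology limits of section 3.3.2, in the platelet threshold of section 4.5.4.3, and in the microgram entry of the abbreviation list (section 10). A reading fault is possible, but it is not the better explanation.

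**The case against.** The strongest reply has four parts.

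1. **The source file may be right.** The suspected error turns on a single character. The surviving micro symbols are mostly laboratory units, with one table entry, and they are not all rendered in the same form. None is a microgram dose in running text, so they are imperfect evidence. This stands as a caveat. It is why the conclusion is limited to the text as printed, and why the first step is to look at the source file.

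2. **The text binds nobody.** It is an example within one possible regimen, physician discretion is stated, and the label is cited nearby. All of this is true and lowers the risk. It does not make the figure right, and the label referral is in the carboplatin-or-cisplatin paragraph and is not repeated beside the figure.

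3. **Few, if any, participants would be exposed.** Platinum choice is the investigator's, cisplatin is ruled out below 60 mL/min creatinine clearance, and oral granisetron and ondansetron are offered as alternatives. The gap between 2 mg and several hundred milligrams should itself prompt a check. The documents do not say how many participants receive cisplatin or IV granisetron, so only the bounds of 0 and about 465 can be given, and the upper bound is not an estimate. Exposure may also have ended: planned accrual is 26 months, platinum stops after six 3-week cycles (6 × 3 = 18 weeks), and the SAP dates Revised Protocol 05 to 19 December 2020. The date of first randomization and the recruitment status are not given, so this cannot be settled either way.

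4. **The trial result does not depend on it.** Conceded in full. No endpoint, analysis or dose-modification rule uses granisetron.

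**Conclusion.** The point holds. As printed, the oral and IV granisetron doses are incompatible by a factor of 250 to 500 at 50–100 kg (200 to 600 at 40–120 kg), and no other text corrects them. At least one figure or unit is very probably wrong. The documents do not show which, and no replacement value is asserted here.

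The body weights are assumed, but no plausible adult weight changes the conclusion. Confidence is medium, because a fault in reading the PDF cannot be fully excluded.

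The consequence is a conditional safety risk. It arises only if an Arm B participant receives cisplatin, the site follows this optional example with IV granisetron, and the figure is used without a label check. Statistical inference is unaffected. It should still be corrected, because it is a printed dose in the treatment section of a control arm.

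**What to change.** Check the source file to confirm that the unit is printed as mg/kg. If it is, remove the granisetron figures and say instead that agent, dose and route follow the local product label, in line with the referral already given for carboplatin or cisplatin. Alternatively, keep the example and correct the IV dose and unit after checking the label.

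Notify sites by administrative letter. The protocol has already used this route for small changes: Administrative Letter 05 added an abbreviation, along with personnel changes. Under section 9.1.1, investigators would have to inform their ethics committees of the letter. The cost is otherwise one phrase, with no effect on design, data or analysis. How urgent the letter is depends on whether any Arm B participant is still to receive cisplatin, which the sponsor can establish.

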4.5.2 Dose Delays

Recommendations for dose modifications for EXTREME regimen should be considered with local institutional standards.

4.5.2.1 Nivolumab and Ipilimumab (Arm A)

Dose delay criteria apply for all drug-related AEs. Treatment delay is up to 6 weeks for nivolumab and up to 12 weeks for ipilimumab from the last dose are allowable (any dose delays greater than these will require approval from the medical monitor). It is permissible in cases of a dose held due to AE to skip the dose in the cycle in order to bring the patient back on track with the next Cycle visit.

Tumor assessments for all participants should continue as per protocol even if dosing is delayed.

Nivolumab and ipilimumab administration should be delayed for the following:

- Grade 2 non-skin, drug-related AE, with the exception of fatigue
- Grade 2 drug-related creatinine, AST, ALT and/or Total Bilirubin abnormalities
- Grade 3 skin, drug-related AE
- Grade 3 drug-related laboratory abnormality, with the following exceptions:
 - Grade 3 lymphopenia or asymptomatic amylase or lipase does not require dose delay
 - Grade ≥ 3 AST, ALT, Total Bilirubin will require dose discontinuation (see section 4.5.5)
- Any adverse event, laboratory abnormality, or intercurrent illness which, in the judgment of the investigator, warrants delaying the dose of study medication.
- Participants receiving ipilimumab in combination with nivolumab that have drug-related toxicities that meet the criteria for dose delay, should have both drugs (ipilimumab and nivolumab) delayed until retreatment criteria are met. (Exceptions apply to the retreatment criteria after dose delay of ipilimumab and nivolumab for Grade ≤ 3 amylase and lipase

abnormalities that are not associated with symptoms or clinical manifestations of pancreatitis and that are attributed to ipilimumab alone.)

- Participants who require delay of nivolumab should be re-evaluated weekly or more frequently if clinically indicated and resume nivolumab dosing when re-treatment criteria are met.

Rescheduling:

- Nivolumab may be delayed until the next planned ipilimumab dose if the next ipilimumab dose is scheduled within the next 12 days. This will permit periodic ipilimumab dosing to be synchronized with nivolumab dosing.
- Ipilimumab should be dosed at the specified interval regardless of any delays in intervening nivolumab doses. However, in order to maintain periodic synchronized dosing of ipilimumab and nivolumab, the dosing days of nivolumab and ipilimumab may be adjusted within the permitted ± 3 day window, as long as consecutive nivolumab doses are given at least 12 days apart. Ipilimumab may be delayed beyond the 3 day window if needed to synchronize with the next nivolumab dose.
- If an ipilimumab dose is delayed beyond 6 weeks from the prior ipilimumab dose, then subsequent ipilimumab doses should be rescheduled to maintain the 6 week interval between consecutive ipilimumab doses.
- A dose delay of ipilimumab which results in no ipilimumab dosing for > 12 weeks requires ipilimumab discontinuation, with exceptions as noted in [Section 4.5.5.2](#).

For both nivolumab and ipilimumab: A dose given more than 3 days after the intended dose date will be considered a dose delay. Longer delays may be allowed following discussion with the Study Director/Medical Monitor.

4.5.2.2 EXTREME Regimen

It is permissible in cases of a dose held due to AE to skip the dose in the cycle in order to bring the patient back on track with the next Cycle visit. Cetuximab, cisplatin, carboplatin, and 5-FU should be delayed for the following:

- Presence of febrile neutropenia or neutropenia < 1500 cells/mm³ for greater than one week despite the use of Growth factors
- Any Grade ≥ 2 non-skin, drug-related adverse event, except for alopecia, fatigue or laboratory abnormalities
- Any Grade 3 skin drug-related AE
- Any Grade 3 drug-related laboratory abnormality, with the following exceptions:
 - Grade 3 lymphopenia does not require a dose delay
 - Delay if total bilirubin $> 1 \times$ ULN or if AST and/or ALT $> 1.5 \times$ ULN occurs concomitant with alkaline phosphatase $> 2.5 \times$ ULN
- Any AE, laboratory abnormality or inter-current illness which, in the judgment of the investigator, warrants skipping the dose of study medication.

Subsequent dose reductions may be required as per [Section 4.5.3.2](#). Participants may receive growth factors (including G-CSF and erythropoietin) at the discretion of the investigator.

A dose given more than 3 days after the intended dose date will be considered a dose delay. A maximum delay of 6 weeks between doses is allowed. Longer delays may be allowed following discussion with the Medical Monitor.

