- One exception to note is when ipilimumab and nivolumab doses are delayed due to drug-related Grade ≥ 3 amylase or lipase abnormalities not associated with symptoms or clinical manifestations of pancreatitis. If the investigator assesses the Grade ≥ 3 amylase or lipase abnormality to be related to ipilimumab and not related to nivolumab, nivolumab may be resumed when the amylase or lipase abnormality resolves to Grade < 3 but ipilimumab may only be resumed when the amylase or lipase abnormality resolves to Grade 1 or baseline. Investigator attribution of this toxicity to the ipilimumab dosing must be clearly noted in the participant's medical chart. The BMS Medical Monitor should be consulted prior to resuming nivolumab in such participants.

4.5.4.3 **Criteria to Resume Chemotherapy Dosing (Arm B)**

Participants may resume treatment with study drug when the drug-related AE(s) resolved or returned to baseline value, with the following exceptions below.

- Participants may resume treatment in the presence of ANC $\geq 1500 / \text{mm}^3$ and Platelets $\geq 100 \times 10^3 / \mu\text{L}$
- Participants may resume treatment in the presence of Grade 2 fatigue.
- Participants who have not experienced a Grade 3 drug-related skin AE may resume treatment in the presence of Grade 2 skin toxicity.
- Participants with baseline Grade 1 AST/ALT or total bilirubin who require dose delays for reasons other than a 2-grade shift in AST/ALT or total bilirubin may resume treatment in the presence of Grade 2 AST/ALT OR total bilirubin.
- Participants with combined Grade 2 AST/ALT AND total bilirubin values meeting discontinuation parameters (Section 4.5.5.3) should have treatment permanently discontinued.
- Drug-related pulmonary toxicity, diarrhea, or colitis, must have resolved to baseline before treatment is resumed.
- For Cetuximab:
 - Pulmonary Toxicity: Permanently discontinue for confirmed interstitial lung disease.
 - Skin Reaction: If a participant experiences a Grade 3 skin reaction, cetuximab therapy is to be withheld for up to 2 consecutive infusions; the dose level should not be changed. The investigator can also consider concomitant treatment with topical and/or oral antibiotics; topical corticosteroids are not recommended. If the toxicity resolves to Grade 2 or less within 2 weeks, treatment may resume. For repeat occurrences of a Grade 3 skin reaction, see Table 4.5.3.2-1 above.

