4.5.5.3 EXTREME Regimen Dose Discontinuation (Arm B)

Treatment should be permanently discontinued for the following:

- Any drug-related Grade 4 toxicity including laboratory abnormalities the subject will be discontinued from the relevant study drug, with the following exceptions:
 - Isolated Grade 4 electrolyte abnormalities not associated with clinical sequelae and are adequately managed and corrected within 72 hours of onset.
 - Grade 4 neutropenia or lymphopenia ≤ 7 days
- Any Grade 3 non-skin, drug-related adverse event lasting > 7 days, with the following exceptions:
 - Grade 3 drug-related laboratory abnormalities do not require treatment discontinuation, except for the following scenarios:
 - ◆ Grade 3 drug-related thrombocytopenia associated with bleeding
 - ◆ Any of the following drug-related liver function test (LFT) abnormalities:
 - AST or ALT > 8 x ULN
 - Total bilirubin > 5 x ULN
 - Concurrent AST or ALT > 3 x ULN and total bilirubin > 2 x ULN
 - ◆ Calculated creatinine decreases to < 60 mL/min based on Cockcroft Gault formula on participants receiving cisplatin. Switch to carboplatin is allowed at the discretion of investigator for the remaining cycles. See re-treatment criteria [section 4.5.4.3](#)
 - Any dosing delay lasting > 6 weeks, with the following exceptions:
 - If local standards allow dosing delays > 6 weeks for drug-related AEs, contact the BMS Medical Monitor prior to re-initiating treatment.
 - Dosing delays > 6 weeks that occur for non-drug-related reasons may be allowed if approved by the BMS Medical Monitor. Prior to reinitiating treatment in a participant with a dosing delay lasting > 6 weeks, the BMS Medical Monitor must be consulted. Tumor assessments should continue as per protocol even if dosing is delayed.
- Any adverse event, laboratory abnormality, or intercurrent illness which, in the judgment of the Investigator, presents a substantial clinical risk to the participant with continued treatment.

Participants who discontinue one of the study drugs in Arm B may, at the investigators discretion, continue administration of the other study drugs. For example, if 5-FU is discontinued, cetuximab and platinum agent may be continued at the intended dose and schedule.

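### Arm B lists no hold or discontinuation for short, afebrile Grade 4 neutropenia although milder Grade 3 neutropenia must be held, and the neighbouring count rules do not agree

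*Protocol*

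**What the plan says.** Four parts of the protocol govern Arm B dosing at low blood counts.

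- **Hold (4.5.2.2).** The neutropenia bullet reads "Presence of febrile neutropenia or neutropenia < 1500 cells/mm³ for greater than one week despite the use of Growth factors". A general bullet covers "Any Grade ≥ 2 non-skin, drug-related adverse event, except for alopecia, fatigue or laboratory abnormalities", so it leaves laboratory values out. The laboratory bullet covers "Any Grade 3 drug-related laboratory abnormality, with the following exceptions"; its exceptions are lymphopenia and a liver-test rule. A last bullet is discretionary: "Any AE, laboratory abnormality or inter-current illness which, in the judgment of the investigator, warrants skipping the dose of study medication".
- **Dose reduction (Table 4.5.3.2-3).** Based on the nadir since the last administration, 5-FU and platinum drop one level for, among others, ANC below 500/mm³ lasting 5 days or more, and Grade 4 hemoglobin (below 6.5 g/100 mL).
- **Restart (4.5.4.3).** The general rule is "Participants may resume treatment with study drug when the drug-related AE(s) resolved or returned to baseline value, with the following exceptions below". The first exception begins "Participants may resume treatment in the presence of ANC" and gives limits of 1500/mm³ for ANC and 100 x 10³/µL for platelets, with no condition on duration or growth factors.
- **Discontinuation (4.5.5.3).** Any drug-related Grade 4 toxicity, laboratory values included, stops the relevant drug. One exception is "Grade 4 neutropenia or lymphopenia" of 7 days or less; the other is isolated, promptly corrected electrolyte abnormalities.

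The opening line of 4.5.2 adds that EXTREME dose modifications are to be considered alongside local institutional standards.

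**The concern.** Naming only Grade 3 in a hold rule is safe if every Grade 4 value goes to discontinuation. Section 4.5.5.3 breaks that link for short Grade 4 neutropenia, so a worse count can carry no listed action while a better one requires a hold. That is an odd result for a safety rule in a platinum/5-FU regimen.

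Two neighbouring points suggest that the sections were not read against each other. Grade 4 hemoglobin has two different prescribed actions, and it is not clear when the restart count limits apply.

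At stake is clear and consistent dosing of the control arm in an open-label trial. If sites fill the gap differently, Arm B delays and reductions, which SAP Sections 7.4.2 and 7.6.4 summarise, will partly reflect how each site read the protocol.

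**Working it through.** No arithmetic in the plan is involved. The check sets the lists side by side.

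**1. Short Grade 4 neutropenia.** Take drug-related, afebrile neutropenia and apply only the listed, non-discretionary criteria.

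| Case | 4.5.2.2 neutropenia bullet | 4.5.2.2 laboratory bullet | 4.5.5.3 | Listed action |
|---|---|---|---|---|
| Grade 3, 7 days or less | Not met (needs more than one week) | Met | Not met | Hold |
| Grade 4, 7 days or less | Not met (needs more than one week) | Not met (names Grade 3) | Exempt | None |
| Grade 4, more than 7 days | Met if growth factors were used | Not met | Met | Discontinue the relevant drug |

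The general adverse-event bullet does not help, because it excludes laboratory abnormalities. If neutropenia counted there, every Grade 2 case would be held and the conditions in the neutropenia bullet would have no purpose. No other section sets a minimum count: Table 5.1-2 asks for laboratory tests within 72 hours before Day 1, but neither it, nor 4.5.1.2, nor Table 4.5-1 says what count permits treatment.

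This result uses grades and durations only. Wherever the boundary between Grade 3 and Grade 4 lies, crossing it downward removes the listed hold for up to 7 days. For illustration, the protocol names CTCAE v4.0 but does not print its cut-offs, so assume Grade 3 is 500 to below 1000/mm³ and Grade 4 is below 500/mm³:

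- ANC 800 for 3 days: hold.
- ANC 400 for 4 days: no listed hold, no discontinuation (4 ≤ 7), no dose reduction (4 < 5).
- ANC 400 for 7 days: no listed hold, no discontinuation (7 ≤ 7). Table 4.5.3.2-3 lowers the dose level (7 ≥ 5), but that sets how much is given, not whether Day 1 goes ahead.

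**2. Neutropenia bullet against laboratory bullet.** The first requires more than a week despite growth factors. The second holds Grade 3 neutropenia at any duration. They give different answers for short Grade 3 neutropenia, and the text does not say which governs.

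**3. Grade 4 hemoglobin.** Table 4.5.3.2-3 lowers the dose by one level. Section 4.5.5.3 stops the relevant drug for drug-related Grade 4 laboratory values, and hemoglobin is not among its exceptions. No outside cut-off is needed to see this conflict.

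**4. Scope of the restart limits.** Take ANC 1400 for 3 days with platelets 120 x 10³/µL, which meets no listed hold if 1400 is above Grade 3 (same assumption).

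- If the limits condition every restart, a participant held for another toxicity could not resume at this count.
- If the bullet only relaxes return to baseline after a low-count hold, that participant could resume once the other toxicity had resolved.

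The text supports either reading. Entry required ANC of at least 1500/µL and platelets of at least 100 x 10³/µL (3.3.2), so the baseline route does not normally lower the limits.

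**The case against.** **Sites are not obliged to dose.** The discretionary bullet names laboratory abnormalities, 4.5.2 and 4.5.3.2 point to local standards, and 4.5.1.2 lets doses be delayed according to tolerance. Many sites would hold in practice. This stands, and it limits the seriousness. It does not supply a stated action.

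**Grade 3 may be shorthand for Grade 3 or worse.** Arm A's list (4.5.2.1) also uses bare grades. This is plausible, but the Arm B list uses an at-least sign for Grade 2 two bullets earlier, so a reader cannot tell.

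**The specific neutropenia bullet may override the general laboratory bullet.** Then short Grade 3 neutropenia would not be held either and the inversion would disappear. But the laboratory bullet lists its exceptions, and neutropenia is not one of them.

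**Hold and restart limits may differ on purpose.** A reader might infer that 4.5.2.2 and 4.5.4.3 contradict each other because one count gives opposite instructions depending on whether the participant is already on hold. The documents do not support that. The general skin rules in both arms hold at Grade 3 but allow restart at Grade 2 only if there was no earlier Grade 3 skin event. Arm A laboratory values are generally held at Grade 3 and restart at Grade 1 or baseline (4.5.2.1, 4.5.4.1). The count bullet in 4.5.4.3 is also a permission listed among exceptions; where that section imposes a requirement, as for pulmonary toxicity, it says so. What remains is the unclear scope of the bullet, not a contradiction.

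**Conclusion.** Read literally, drug-related, afebrile Grade 4 neutropenia of 7 days or less has no listed hold or discontinuation in Arm B, while Grade 3 must be held. This rests on the printed grades and durations; only the numerical examples rest on assumed CTCAE cut-offs. The Grade 4 hemoglobin conflict is also on the page. The restart limits are ambiguous in scope rather than inconsistent.

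A reader might infer that short Grade 4 neutropenia never triggers a hold. That goes too far: febrile neutropenia is held by name, and the investigator may hold any case.

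On size, 930 participants randomized 1:1 gives 930 / 2 = 465 in Arm B, each with up to 6 platinum/5-FU cycles. These are the participants and cycles subject to the rules, not the number affected; the documents give no frequency and no evidence that control-arm exposure has shifted. No sample size, power or alpha figure changes. This is a wording fault in a safety rule, worth correcting because the correction is cheap.

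**What to change.** Reconcile Sections 4.5.2.2, 4.5.4.3 and 4.5.5.3 and Table 4.5.3.2-3 so that:

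- each Grade 3 and Grade 4 laboratory value has one consistent stated action, including Grade 4 values exempt from discontinuation and Grade 4 hemoglobin;
- the text says how the neutropenia bullet and the laboratory bullet in 4.5.2.2 relate;
- 4.5.4.3 says whether its ANC and platelet limits apply to every restart or only after holds for low counts, and how they relate to the neutropenia bullet in 4.5.2.2.

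The sponsor's clinical team decides which limits and actions apply, and whether hold and restart limits should differ.

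The cost is a protocol wording change. The downside is that some cycles may be handled differently from current site practice. The statistical plan is unaffected.
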